5.6 Process evaluation

We will carry out a mixed methods process evaluation guided by the new MRC Framework²⁶ for developing and evaluating complex interventions to:

- understand acceptability and a qualitative understanding of adherence to the intervention, and issues around implementation.
- explore participants' and HCPs/trial recruiter's views on the trial processes including a qualitative overview of local site adaptations and contextual factors influencing trial delivery, and views on trial materials and processes (e.g. recruitment, consent and retention).

6 Trial design and setting

The VESPER Trial is a pragmatic, three-arm, multi-site, open-label, patient-randomised superiority trial with internal pilot, qualitative and economic evaluations comparing two intravesical treatments for the prevention of rUTI in women both directly and to the current guideline-recommended standard of second line daily oral antibiotics, during a 6-month treatment and 6-months post-treatment follow-up period.

The two intravesical treatment arms are intravesical antibiotics – 80mg of Gentamicin diluted to 50ml using normal saline and intravesical GAG replacement compounds (a range of agents are permitted including: laluril, Cystistat, Gepan). The daily oral antibiotics arm will use guideline recommended antibiotics which will include, but not be limited to; Nitrofurantoin (50/100mg), Trimethoprim (100mg), Amoxicillin (250mg) or Cefalexin (125/250mg once a day)

We will randomise participants using a 1:3:3 ratio using the covariate-adaptive randomisation procedure following the Pocock and Simon's minimisation method with an 80% random element^{27, 28}. Allocations will be minimised by previous UTI frequency (<=4/year; >4/year) and menopausal status (pre; peri/post), both of which have strong prognostic value. We require 412 participants in total (62 in the oral comparator arm and 175 in both intravesical experimental arms) as we are primarily interested in comparisons of each intravesical prophylaxis against standard care and then a head-to-head comparison of intravesical prophylaxes.

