9.6.2 Randomisation

Randomisation will be in a 1:3:3 ratio to receive: (1) Oral antibiotic prophylaxis (2) Intravesical Gentamicin (3) Intravesical GAG replacement for 6 months. To reduce the risk of imbalance of key covariates, the Pocock and Simon's minimisation method with an 80% random element will be used for previous UTI frequency (<=4/year; >4/year) and menopausal status (pre; peri/post) (see Section 15.1).

If a participant does not respond to their initially allocated prophylaxis or they experience intolerable side-effects, they can be re-randomised to one of the remaining two prophylactic regimes. Rerandomisation will be based on a 1:1 ratio. Re-randomisation will be based on block randomisation (see Section 15.1). If a participant does not respond to treatment following re-randomisation then they would be permitted to switch to the third treatment arm without the need for any further randomisation. If a participant is re-randomised to a different arm, their treatment will start back to time zero ie if a participant gets re-randomised at the end of their 6-months treatment period, they would be on the new treatment for a further 6-months.

Computerised web-based remote randomisation (available 24 hours a day) will be used. The randomisation system will be built by the in-house CTR information Systems and Technology Solutions team (TMS2). The CTR Trial team will also be notified that a participant has been randomised or rerandomised via an automated e-mail alert mechanism to the VESPER email inbox.

In the event that the online randomisation system is unavailable at site, or the site has problems accessing the online website, then the local investigator may contact the CTR (during office hours). Manual randomisation may be performed by CTR staff on request of the local investigator.

If the online system does not work, a telephone back-up managed by the CTR Trial team will be available for use during office hours Monday to Friday: 08:30-16:00.

For online randomisation: A randomisation/re-randomisation form must be completed on the trial database to randomise the participant.

For telephone randomisation: A randomisation/re-randomisation form must be completed before telephoning the randomisation line.

10 Withdrawal & lost to follow-up

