15.3 Sample size

We aim to recruit 412 participants over 21 months and follow them up for a fixed 12-month period (62 in the oral comparator arm and 175 in both intravesical experimental arms). We are primarily interested in comparisons of each intravesical prophylaxis against standard care and then a head-to-head comparison of intravesical prophylaxes.

Two sets of comparisons are powered. The first set compares each intravesical prophylaxis arm to the second-line prophylactic oral antibiotics arm to detect a difference in the UTI rate of 1 (assumed UTI rate of 2 from previous studies³). This is calculated based on 90% power, and two-sided alpha of 0.05 (no multiplicity adjustment as comparisons is considered independent). This comparison requires 62 participants in each arm (1:1:1 ratio). The second set is to detect a difference in the UTI rate between the intravesical arms. This is calculated based on 90% power, 5% two-sided alpha (no adjustment as we are making this comparison as part of a fixed sequence. That is, we will only compare the intravesical prophylaxis arms head-to-head if both are superior to the second-line prophylactic oral antibiotics arm), with target effect size of 30% (i.e. a relative difference of 30% between intravesical arms, with an assumed UTI rate of one in one of the intravesical arms). This comparison requires 175 in each intravesical arms and hence 1:3:3 ratio.

Target differences between oral and intravesical treatments are based on PPI work. In line with previous studies³ the PPI group for VESPER overwhelmingly stated that any intravesical treatment demonstrating a reduction in UTI frequency of 1 episode per year greater than oral antibiotic tablets would be considered superior. Target differences between intravesical treatments are based on our clinician survey administered via UKCS which revealed that the majority of clinicians felt that for one intravesical treatment to be considered superior to another there would need to be a 30% or greater difference in efficacy. This sample size is further inflated to account for a 15% drop-out (as observed in the ALTAR trial³).

Although we are proposing a SMART design, our primary interest is the marginal effect of the initial prophylaxis, the comparison of each treatment sequence is considered exploratory and hence the SMART design has no impact on our required sample size.

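### Section 15.3 says the sample size was inflated for 15% drop-out, but the target of 412 is exactly the stated requirements added up (62 + 175 + 175) and does not match the 1:3:3 ratio

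*Protocol*

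**What the plan says.** Section 15.3 of the protocol powers two sets of comparisons at 90% with two-sided alpha 0.05.

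- **Oral versus each intravesical arm:** the target is "to detect a difference in the UTI rate of 1 (assumed UTI rate of 2 from previous studies", and the result is "This comparison requires 62 participants in each arm (1:1:1 ratio").
- **Head-to-head:** a 30% relative difference with a rate of one in one arm. The result is "This comparison requires 175 in each intravesical arms and hence 1:3:3 ratio".

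After both results the section adds: "This sample size is further inflated to account for a 15% drop-out". The recruitment target, in 15.3 and in section 6, is "We require 412 participants in total (62 in the oral comparator arm and 175 in both intravesical experimental arms"). Section 9.6.2 fixes the allocation: "Randomisation will be in a 1:3:3 ratio", with oral antibiotics as the 1.

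Sections 15.4 and 16.1 bring women with incomplete follow-up into the primary analysis by multiple imputation.

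**The concern.** A size that a comparison requires and that is then further inflated should end above the requirement. Here the requirement and the recruitment target are the same numbers in every arm. The arm sizes also do not follow from the allocation ratio. The requirement, the inflation and the ratio therefore cannot all be right as written.

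A reader cannot tell whether 62 and 175 are sizes before or after drop-out, or how many oral women the randomisation is expected to deliver. The oral arm is the shared control for both primary comparisons. The intravesical arms carry the head-to-head, whose requirement set the trial's size. If no allowance for drop-out was made, the 90% power quoted for the head-to-head is not what the design delivers.

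**Working it through.** **Inputs.** From 15.3: 62, 175, 412, 15% drop-out, 90% power, two-sided 0.05, oral rate 2 with a difference of 1, and a 30% difference from a rate of one. From 9.6.2: 1:3:3. From 5.3: a 6-month primary outcome window.

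**Step 1: the plan's 62.** Assume the rates 2 and 1 are annual, because 15.3 ties the target to "a reduction in UTI frequency of 1 episode per year greater than oral antibiotic tablets". Over 6 months the means are then 1 and 0.5. With (1.960 + 1.282)² = 10.507, the Poisson requirement per arm at 1:1 is:

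- square-root scale: 10.507 / [2(√1 − √0.5)²] = 61.2
- rate difference: 10.507 × (1 + 0.5) / 0.5² = 63.0
- log rate ratio: 10.507 × (1/1 + 1/0.5) / (ln 2)² = 65.6

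So 62 is reproduced with no drop-out allowance. It is also reproduced with one: the log-rate form with the null variance at the control rate gives 51.9, and 52/0.85 = 61.2, which rounds up to 62.

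**Step 2: is there inflation in the total?**

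| | Oral | Each intravesical | Total |
|---|---|---|---|
| Stated requirement | 62 | 175 | 412 |
| Recruitment target | 62 | 175 | 412 |
| Requirement / 0.85 | 73 | 206 | 485 |

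None is visible.

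**Step 3: does the ratio fit?** 175/62 = 2.82, so the stated sizes are 1:2.8:2.8. At 1:3:3, 412/7 = 58.9 oral and 3 × 412/7 = 176.6 per intravesical arm, or about 59:177:177.

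**Step 4: expected numbers with complete follow-up.** 58.9 × 0.85 = 50.0 oral; 176.6 × 0.85 = 150.1 per intravesical arm.

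**Step 5: oral-comparison power at 50 v 150.** Poisson log rate ratio, means 1 and 0.5:

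- SE = √[1/(50 × 1) + 1/(150 × 0.5)] = 0.183
- power = Φ(0.693/0.183 − 1.960) = 96.7%

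The same formula at 62 v 62 gives 88.3%. With an equal-variance scaling in which 62 v 62 gives 90%, 50 v 150 gives 94.6%. Either way, power at 50 v 150 is above 90%.

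**Step 6: head-to-head power at 150 v 150.** Scale so that 175 per arm gives exactly 90%, which avoids choosing a formula or a time unit:

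- power = Φ(3.242 × √(150/175) − 1.960) = Φ(1.041) = 85.1%

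For comparison, plain Poisson with means of 1 and 0.7 in the window gives 85.7% at 175 per arm and 80.0% at 150.

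**The case against.** **The figures may already include drop-out and simply be badly worded.** This cannot be excluded, since 62 is also 52/0.85. A reader might infer that the inflation sentence is proved false; the documents do not go that far. The reading sits badly with the 175, however. For means of 1 and 0.7, the rate-difference form gives 148.3 per arm at 80% power, and 148.3/0.85 = 174.4. At the stated 90%, the usual forms need 197 to 201 before any inflation, and the control-rate-null form needs 179. Even if the reading is right, 15.3 has to say so.

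**Women who drop out are not lost to the analysis.** This stands. Someone might infer that only about 50 oral women are analysed. Sections 15.4 and 16.1 say otherwise: about 59 enter the primary analysis and about 50 have complete data. Imputation does not in general restore all the missing information, and 15.3 itself treats drop-out as something the size must allow for.

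**The need for 62 oral women was derived at 1:1:1.** This stands too. It is tempting to read 50 against 62 as an underpowered oral comparison. With three times as many women in the other arm, 50 oral women give more power than 62 v 62, not less.

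**Three women between 59 and 62 do not matter.** In power terms that is fair, and minimisation with a random element does not fix exact totals anyway. It is still a stated arm size that the stated ratio does not produce.

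**Conclusion.** The point holds as an internal contradiction in the sample-size statement. The requirements, the recruitment target, the 15% inflation and the 1:3:3 ratio cannot all be true together. This follows from the protocol's own figures and needs no modelling assumption.

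The consequence depends on reading 62 and 175 as sizes before drop-out, which is how 15.3 is worded. On that reading, the oral comparisons keep more than 90% power (96.7% under Poisson with assumed 6-month means of 1 and 0.5). The head-to-head drops from the stated 90% to about 85%. That figure counts only women with complete follow-up. If drop-outs contributed full information, 177 per arm would give 90.3% on the same scale, so the true value lies between about 85% and 90%. The documents do not support a claim that the oral comparison is underpowered. The effect is modest, and it falls on the head-to-head.

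**What to change.** In sections 15.3 and 6:

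1. State each arm's size before and after 15% drop-out, consistent with 1:3:3: about 59:177:177 randomised and 50:150:150 with complete follow-up from 412.
2. Correct the inflation sentence or delete it. If 62 and 175 already include drop-out, say so and give the underlying requirements.
3. Restate the power of both the oral comparisons and the head-to-head at those expected numbers and at the actual allocation, in place of the 1:1:1 figure followed by an inflation.

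This changes text only and needs no extra patients. The cost is a less favourable stated head-to-head power, about 85% instead of 90%.

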15.1 Randomisation

Participants will be individually allocated in a 1:3:3 ratio to one of the three trial arms: (1) intravesical gentamicin, (2) intravesical GAG replacement or (3) oral antibiotic prophylaxis for up to 6 months. The covariate-adaptive randomisation procedure following the Pocock and Simon's range method_will be used to minimise the imbalance of key covariates with an 80% random element applied to reduce the risk of subversion. These key minimisation factors are:

- prior frequency of UTI (<= 4 episodes per year or > 4 episodes per year)
- menopausal status (pre-menopausal or menopausal/post-menopausal)

Following randomisation, those in the oral antibiotics arm will be issued with a prescription. For those in the intravesical arms an appointment will be arranged for the participant to come back to clinic for their first instillation.

Participants can be re-randomised to a different prophylactic regime due to lack of efficacy or incidence of predefined adverse events. These include i.) relapse with at least two episodes of UTI occurring in the 6-month treatment period in line with currently accepted definitions of recurrent UTI; ii.) intolerance of side effects of prophylactic antibiotic. In this event, participants will be re-randomised 1:1 between the two remaining allocations. Re-randomisation will be based on block randomisation with no stratification. An individual not otherwise involved with the study will produce the final re-randomisation schedule. The randomisation procedure will be implemented via a webbased remote system (TMS2 - available 24 hours a day) that bult in-house CTR Information Systems and Technology Solutions team with telephone back-up as described in Section 9.5.2. Full details will be provided in a separate randomisation protocol.

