16.1 Main analysis

Descriptive statistics will be summarised using frequencies and percentages, means and standard deviations, or medians and interquartile ranges as appropriate. Recruitment, retention, and other trial processes (e.g. adherence to allocation) will be reported both overall, by arm, and disaggregated by site, menopausal status, previous UTI frequency, and previous type of failed treatment.

The primary analysis will be an intention to treat, including all randomised participants regardless of adherence or discontinuation of the initial treatment allocation or initiation of the subsequent treatment.

For the clinical-effectiveness primary outcome (rate of symptomatic, antibiotic-treated UTI, selfreported by participants from randomisation to the 6-month treatment period (verified from medical

Canolfan

records)), a Poisson/negative binomial regression model will be fitted to estimate incidence rate ratios, including fixed effects for allocation, covariate factors used in randomisation (prior frequency of UTI and menopausal status) and random effects to model heterogeneity between sites. Regression analysis results will be presented as point estimates with confidence intervals and p-values. The primary estimand for VESPER is below:

Primary clinical question: In women who fail first-line preventative treatment for rUTI, does the strategy to initially prescribe intravesical treatments result in a greater reduction in the rate of symptomatic UTIs over the subsequent 6 months compared to the current guideline-recommended second-line prophylactic antibiotic therapy?

The estimand is described by the following attributes:

- Population: women aged >16years with recurrent uncomplicated UTI who have failed firstline treatments requiring second-line prophylactic treatment and able to receive intravesical treatments and take second-line oral antibiotic prophylaxis.
- **Endpoint**: rate of symptomatic UTIs from randomisation to 6-months. •
- **Treatment condition**: The intravesical treatments and second-line oral antibiotic prophylaxis, regardless of adherence or discontinuation of the initial treatment allocation or initiation of the subsequent treatment (via re-randomisation) (treatment policy strategy);
- Remaining intercurrent events: Treatment adherence or discontinuation or initiation of the subsequent treatment are covered by previous attribute.

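### The statement that the SMART design leaves the sample size untouched does not follow, because re-randomisation inside the 6-month primary window can move the treatment-policy effect towards the null

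*Protocol*

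**What the plan says.** Section 15.3 sizes two comparisons. The first is each intravesical arm against oral antibiotics, to "detect a difference in the UTI rate of 1 (assumed UTI rate of 2 from previous studies"); it gives 62 per arm. The second is head-to-head, for "a relative difference of 30% between intravesical arms, with an assumed UTI rate of one in one of the intravesical arms"; it gives 175 per intravesical arm. The section names the marginal effect of the initial prophylaxis as the primary interest and concludes that "the comparison of each treatment sequence is considered exploratory and hence the SMART design has no impact on our required sample size".

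Section 16.1 defines the primary endpoint as the UTI rate from randomisation to 6 months under a treatment-policy strategy, "regardless of adherence or discontinuation of the initial treatment allocation or initiation of the subsequent treatment (via re-randomisation").

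Section 15.1 allows re-randomisation for intolerance or for "relapse with at least two episodes of UTI occurring in the 6-month treatment period", 1:1 to the two remaining arms. Section 9.6.2 says the same in general terms, and Section 11.5 adds changed liver tests on oral antibiotics. None of them sets a waiting time. The only worked example, in Sections 6 and 9.6.2, is a switch at the end of the 6 months.

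**The concern.** The quoted sentence joins two different matters. Exploratory comparisons of treatment sequences need no extra women, and that part is correct. But re-randomisation before month 6 also changes what is observed in the original arms, and the primary analysis compares those arms as randomised.

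The direction follows from the allocation rule. Every re-randomised oral failure goes to an intravesical arm, assumed to have the lower rate. Half of the re-randomised intravesical failures go to oral, assumed to have the higher rate. The arm with more UTIs also reaches the two-UTI trigger more often. The marginal rates therefore converge. If 2, 1 and 0.7 describe women who stay on their first treatment, the stated power belongs to a larger effect than the one the analysis will estimate.

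**Working it through.** **Inputs from the protocol.** Rates 2 (oral), 1 and 0.7 (intravesical); two-sided 5%; arms of 62 and 175; 15% loss, so 0.85 × 62 = 53 and 0.85 × 175 = 149; trigger at two UTIs; 1:1 to the other arms; 6-month window. The time unit of the rates is not given where they are stated. The patient-group target is per year ("a reduction in UTI frequency of 1 episode per year greater than oral antibiotic tablets would be considered superior"), so both readings are shown.

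**Assumptions, not in the protocol.** Every woman with two UTIs is re-randomised, either at once or one month later (one sixth of the window). The new arm's rate applies immediately. Intolerance switches are left out.

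**The plan's own figures first.** The Poisson log-ratio formula is n = (1.96 + 1.282)² × (1/μ₁ + 1/μ₂) / (ln μ₁/μ₂)².
- Oral comparison, annual rates over 6 months (1 vs 0.5): 10.51 × 3 / 0.4805 = 65.6. A square-root formula gives 10.51 × 0.5 / (1 − √0.5)² = 61.2, hence 62, but only before the 15% inflation.
- Head-to-head (1 vs 0.7): 10.51 × 2.429 / 0.1272 = 201 before inflation. 175 does not reproduce at 90% power. It does at 80% power divided by 0.85 (174.4 by the rate-difference formula).

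These mismatches are a separate matter. They explain why the starting powers below are not 90%.

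**Effect of switching on the mean count.** Let λ be the first-stage rate per window, λ′ the mean rate of the two destination arms, and d the delay as a fraction of the window. The expected share of the window spent on the new treatment is

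R = (1 − d) − [2 − (2 + λ(1 − d)) e^(−λ(1 − d))] / λ, and the mean count is λ + (λ′ − λ)R.

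For an immediate switch, R is 0.271 at λ = 2, 0.104 at λ = 1, 0.058 at λ = 0.7, 0.033 at λ = 0.5 and 0.017 at λ = 0.35.

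Oral vs intravesical (both intravesical arms at rate 1):
- Rates per 6 months: oral 2 − 1 × 0.271 = 1.729; intravesical 1 + 0.5 × 0.104 = 1.052; ratio 0.61. With a one-month delay: 1.820 and 1.032; ratio 0.57.
- Annual rates: oral 1 − 0.5 × 0.104 = 0.948; intravesical 0.5 + 0.25 × 0.033 = 0.508; ratio 0.54. With the delay: 0.968 and 0.505; ratio 0.52.

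Head-to-head, immediate switch:
- Rates per 6 months: 1 + 0.35 × 0.104 = 1.036 and 0.7 + 0.8 × 0.058 = 0.747; ratio 0.70 becomes 0.72.
- Annual rates: 0.5 + 0.175 × 0.033 = 0.506 and 0.35 + 0.4 × 0.017 = 0.357; ratio 0.70 becomes 0.71.

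With an immediate switch, the share re-randomised in the window is 1 − e^(−λ)(1 + λ): 59% of oral and 26% of intravesical women (rates per 6 months), or 26% and 9% (annual).

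**Power.** Power = Φ(|ln ratio| / SE − 1.96), with SE² = v₁/(m₁²n₁) + v₂/(m₂²n₂). Counts after switching are not Poisson, so the variances v come from simulating the same process. A range runs from an immediate switch to a one-month delay.

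| Comparison, no overdispersion | No switching | With switching |
|---|---|---|
| Oral, annual, 62 vs 175 | 99% | 97–98% |
| Oral, annual, 53 vs 149 | 97% | 94–96% |
| Oral, per 6 months, 53 vs 149 | >99% | 98–>99% |
| Head-to-head, per 6 months, 175 per arm | 86% | 74–79% |
| Head-to-head, annual, 175 per arm | 57% | 53–56% |

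Section 16.1 allows for a negative binomial model but gives no dispersion. With an assumed dispersion of 0.5 and annual rates, oral-comparison power at 62 vs 175 falls from 94% to 84–89%.

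**The case against.** **The targets may already be marginal.** Section 15.3 bases them on a patient group's worthwhile difference and a clinician survey, not on on-treatment estimates, and names the marginal effect as the interest. If 2, 1 and 0.7 are meant as treatment-policy rates, n for those targets stands. This objection holds as far as it goes. The protocol does not say which is meant, and its stated reason is a different one, that sequence comparisons are exploratory.

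**Early switching is permitted, not required.** Women can be re-randomised; uptake and delay cannot be derived, and the one worked example has no effect on the 6-month endpoint. That limits the size of the point but does not remove it. The estimand clause on re-randomisation would be empty if every switch waited until month 6. Section 9.6.2 also allows a move to the third arm after a second failure. With treatment restarting at time zero and a fixed 12-month trial period, switching only at month 6 would leave no room for a third course within follow-up.

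**The oral comparisons have reserve.** This stands: 62 versus 175 absorbs the dilution unless counts are overdispersed. A reader might infer a collapse in oral-comparison power, since 98% can be brought down to 67–69% at 53 versus 149. That needs rates per 6 months, instant and complete switching, and a dispersion of 0.5, which the protocol does not state.

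**Switching is partly covered already.** Section 16.1 plans sensitivity estimands that account for switching, and Section 11.1 offers alternatives on intolerance in any case, so not all dilution is due to the SMART element. Both are correct. Neither supports the sentence on sample size.

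**Conclusion.** The point holds in limited form and should be fixed. That the SMART design has no effect on the required sample size is not supported by the reason given, and it is untrue for any woman re-randomised before month 6 if the assumed rates are those without switching. The direction is towards the null under the protocol's own rates. The size runs from nothing (all switches at month 6) to the losses tabulated above (full uptake, switch within a month of the second UTI).

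The exposed comparison is the head-to-head one. It sets the 175 per arm, and so most of the 412, and has no reserve. It is tested only if both intravesical arms beat oral.

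A reader might go further and infer that the primary analysis estimates a different effect from the one powered, or that the trial is too small because of the SMART design. The documents do not establish either, because the meaning of the rates and the timing of switches are left open. The gap between the starting head-to-head power and 90% exists without any switching and should not be attributed to it.

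**What to change.** In Section 15.3, withdraw the sentence. State the time unit of the rates 2, 1 and 0.7, and whether they are treatment-policy rates that already allow for re-randomisation before 6 months. If they do, that statement is enough. If they do not, restate power for the treatment-policy rate ratio over a stated range of uptake, delay and dispersion, above all for the head-to-head comparison.

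Naming one supplementary switching estimand for the primary outcome is optional, since Section 16.1 already plans estimands of that kind. No change to the clinical switching rule and no added recruitment is proposed. The cost is a short simulation, a few lines of text and, probably, a less favourable stated power.
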